## 1. Purpose of Study and Background

### 1.1 Purpose

The purpose of EQUIPED is to test and evaluate a care quality improvement intervention featuring use of consensus decisional guidance for the medical management of diabetes (DM) patients with Alzheimer's and other forms of dementia (ADRD) in primary care at NYU Langone Health. This quality improvement program will include provider (PCP) workflow enhancements supported by a panel manager (PM) for workflow support, electronic health record (EHR) decision support and feedback, and PCP collaborative learning.

It will test hypotheses about whether care based on explicit standards for DM medical management for people with ADRD will: **H1**) Improve patient symptoms and quality of life while maintaining expected clinical outcomes; **H2**) decrease patient and caregiver management burden and improve care quality based on patient/caregiver preferences; **H3**) (secondary) decrease specialty, ED and hospital utilization.

In order to test and evaluate this program, we will conduct a pragmatic randomized controlled trial (RCT) and evaluate it using mixed methods (surveys and interviews) in 20 NYU Langone Health clinics with the enrollment goal of 500 patients with diagnosed DM and ADRD in the intervention (INT) and control (CON) group (1,000 total).

If EQUIPED demonstrates that patients and family caregivers who receive this quality improvement program achieve established goals for diabetic care in addition to fewer dementia-related symptoms, less caregiver burden and stress, and fewer DM-related adverse events, potentially avoidable and costly utilization may also decrease. This best practice approach could then be widely disseminated to other clinical practices.

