### **INT Clinics:**

In the INT clinics we will introduce the panel manager (PM) to all clinic staff and develop processes for interaction. The PM will work with INT clinic providers to individualize communication methods between the PCP and PM. Each month INT clinic providers will get a list of eligible patients who have appointments with them in the coming month - those with diagnoses of DM-ADRD and those 75 and older with DM who are out of range for HbA1c or BP. This process gives providers monthly reminders about the ongoing quality improvement study and is a more intensive form of QI intervention than provided to CON clinics.

Because this is a pragmatic trial, the clinical team and a project-funded PM will deliver the intervention, fitting it as closely as possible into usual clinical workflow. The clinical team includes PCPs, occasional APNs and PAs (who function as PCPs), RN's, MA's, office staff, and clinic onsite administration. The PM will be part of the team; PMs providing chronic disease self-management support (usually telephonic) are clinic team members in many healthcare systems.

We will assign two PMs to 9 randomly selected INT clinics. Each PM will have 4.5 INT clinics and will engage and focus on their first clinics in a randomly ordered step-wise fashion working within 1-2 clinics over a focused 3-month period before moving on to the next 1-2 clinics for 3 months, then the last 1-2 clinics for 3 months. Our preliminary data suggests 20-50 patients per INT clinic with DM-ADRD  $\geq 65$  years; and about an equal number with DM without ADRD who will screen positive for cognitive impairment, most of whom are  $\geq 75$  years and identified by HbA1c/BP over or under treatment, or identified by provider referral, which we will allow. With 9 INT clinics, given our preliminary data about patient numbers, each PM will have an anticipated 300 dyads. PMs can engage about 33 patients/month, making initial 300 patient/CG contact in 9 months.

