## Measures

### Survey

Table 1		How measured	Subj ect	Baselin e	6 Months	12 months	24 months
Measure	Source of Data						
Age	EHR/ Survey*	Years	CG, Pt	X			
Gender	EHR/ Survey	Categorical: Male/Female	CG, Pt	X			
Race/Ethnicity	EHR/ Survey	Categorical: White, Black, Hispanic, other	CG, Pt	X			

Education	Survey	Categorical: < H.S., H.S., Some College, College graduate+	CG	X			X
Clinical co-morbid conditions	EHR	Charlson comorbidity index 	Pt	X	X	X	X
Medication Complexity	EHR	Unique medications (n) + unique multiple administrations/day (n)	Pt	X	X	X	X
Prior (1-year) non-acute use	ResDAC	Counts: physician ambulatory visits	Pt	X	X	X	X
Prior (1-year) acute use	ResDAC	Counts: ED, hospital visits / bed days	Pt	X	X	X	X
Social Support	Survey	MOS Abbreviated Social Support (4-item; 5-point Likert scale) 	CG	X	X	X	X
COVID-19	Survey	Exposure and symptoms, testing status, impact, changes in burden, access to resources	CG, Pt	X			
Follow-up COVID-19	Survey	Exposure and symptoms, testing status, impact, changes in burden, access to resources	CG, Pt		X	X	X
DM-ADRD-Specific							
Dementia Diagnosis /Type	EMR	Categorical: Yes/No and if yes, AD, Lewy Body disease, Parkinson's Disease, Vascular, Frontotemporal, and mixed	Pt	X			X
Dementia Severity	Survey	Dementia Severity Rating Scale 	Pt	X			X
Caregiver relationship to CR	Survey	Categorical: Spouse, child, other relative, friend/other	CG, Pt	X			

Functional State	Survey	14 items: ADL/ IADL for CG; within DSS for Pt	CG, Pt	X	X	X	X
Marital Status	Survey	Categorical: Single/never married, married, divorced, widowed	CG, Pt	X			X
Substance use history	Survey	Current: Yes/No; Past history: Yes/No	CG, Pt	X	X	X	X
Mental illness history	Survey	Yes/No: Depression, schizophrenia, PTSD, other	CG, Pt	X			
Diabetes care questions	Survey	diet, blood sugar testing, exercise	Pt	X	X	X	X
Hypoglycemia	Survey	Number, number documented, treatment, number seek medical attention	Pt				
Neuropathic pain	Survey	Yes/no	Pt	X	X	X	X
Urinary symptoms	Survey	Counts: frequency, dysuria, incontinence, urgency	Pt	X	X	X	X
Falls	Survey	Number, number injurious in last year and then since last survey, number ED or other falls requiring medical attention	Pt	X	X	X	X
Syncope	EHR	Number, number ED diagnoses or other events requiring medical attention	Pt	X	X	X	X
Structural Measures							
General							
Change in PCP-past 6 mo./last survey	EHR	Yes/No	Pt	X	X	X	X

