Sub-acute care use	ResDAC	Counts: # bed days	Pt	X	X	X	X
LTC use	ResDAC	Counts: # bed days	Pt				
LTAC or Hospice use	ResDAC	Counts: # bed days	Pt				
DM-ADRD-Specific							
Dementia symptoms	Survey	DSS	Pt /CG	X	X	X	X
Diabetes caregiver distress	Survey	Diabetes Caregiver Distress Scale	CG	X	X	X	X

**LEGEND:** CG=Caregiver; Pt=Patient; EHR=Electronic Health Record; ResDAC=Research Data Assistance Center; DM=Diabetes mellitus; ADRD=Alzheimer's disease and related dementias; ADL=Activities of Daily Living; IADL=Instrumental Activities of Daily Living; HABC-M=Health Aging Brain Care-Monitor; PTSD=Post-traumatic Stress Disorder; ED=Emergency Department; PCP=Primary Care Provider; PM=Panel Manager; MYLOH=Managing Your Loved One's Health; MOS=Medical Outcomes Study TBQ= Treatment Burden Questionnaire,\* Note – the survey is always given to the caregiver (CG)

*and includes questions about the CG and about the patient; \*\* Baseline utilization variables will have 20 month look-back through claims and EHR*

As shown in Table 1, many variables for the evaluation will be collected from the EHR or from claims. However, many caregiver-reported variables will also be collected using scales that have been validated for patients, but usually not for caregivers noting that some have been widely used to investigate how a caregiver perceives the patient's conditions. Below we discuss instruments used for caregiver reported variables, as well as the use of EHR and claims to measure patient-related variables. (Table 1 does not reflect the qualitative evaluation. The qualitative study as discussed in Section 3 and elsewhere above, will investigate the experiences of caregivers, patients and providers.)

Variables describing the patients, caregivers and clinics include: a) characteristics of patients and of caregivers, including demographics, marital status, living arrangements, and general health and function; b) patient medical and utilization characteristics, including comorbid conditions, medication complexity, patient symptoms potentially related to diabetes or to medication use and changes, depression and history of substance uses and healthcare utilization in the prior year. Dementia specific characteristics of the patients include type of dementia, its severity, and function. The survey respondent is always the caregiver, although the questions may measure patient or caregiver status.

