We will also measure structure of care variables. These include patient use of consistent PCP care, home health services, and patient insurance. Clinic characteristics are size, support staff number, proportion of Medicare and Medicaid patients. Several baseline variables relate to diabetes but because they are also outcome variables they will be described later. As shown in table 1, many of these baseline and control variables are measured in the EHR and Epic administrative reports, or by claims. Some are measured by validated survey instruments, which are discussed briefly below.

We will collect many process of care measures at baseline and at follow-up. These include: a) provider use of Epic templates and tools; b) provider attendance at educational sessions; c) PM-PCP communication; d) PM-caregiver contact frequency; e) referral for caregiver-support services; f) cognitive screening of diabetes patients over 75; g) change in diabetes medications; h) change in hypertensive medications; i) change in anticholinergic burden; j) change in medication complexity. These variables are measured by EHR review and Epic administrative systems.

Outcome variables include HbA1c level and blood pressure. These variables will be measured at 0, 6, 12 and 24 months when available. Our main outcome is the proportion of patients achieving consensus HbA1c targets. BP will be measured by proportion of patients achieving consensus BP targets per our guideline. These variables will be measured by the EHR.

Utilization outcome variables are ED, hospital, SNF and ambulatory clinic utilization measured by EHR and by claims (for non-New York Langone Health utilization). SNF days must be measured by claims; Epic reports have discharge destination but do not have SNF days. Utilization variables will be measured at 6, 12, 24 months; the baseline measures include a 20 month look back at utilization.

Multiple caregiver reported outcomes about the caregiver and about the patients will also be

collected at 0, 6, 12, 24 months. General outcomes include: a) caregiver perception of care quality (our main caregiver-reported outcome), dyad care goals, preferences, and satisfaction; b) treatment burden; c) caregiver global health. Dementia and diabetes specific outcomes include: a) patient dementia symptoms; b) caregiver diabetes stress.

Below is a brief description of the instruments we will use, all of which have been studied and validated, although not always with caregivers.

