## 7. Data Analysis

We will begin all analyses with descriptive summary statistics and graphical displays of all variables. Continuous variables will be summarized with means, medians, standard deviation and interquartile range; categorical variables will be summarized with frequencies. We will assess the balance by treatment assignment of patients in the INT and CON clinics with respect to demographic and clinical characteristics (e.g., age, gender, Charlson Index, socioeconomic status, baseline TBQ, etc.) using standard tests (t-tests, Wilcoxon rank-sum tests, and  $\chi^2$  tests as appropriate). Any factors that appear to be unbalanced by treatment assignment will be considered as adjustment factors in the primary analyses. All hypothesis testing will be two-sided and conducted using a significance level of 0.05.

The primary outcome of 'on target' HbA1C values will be measured for each patient as a binary indicator. The primary analysis will use a generalized linear mixed model approach, with a logit link, for the probability of being 'on target.' The treatment group (CON vs INT) will be the primary fixed effect of interest; we will also include the practice as a random effect to accommodate clustering of patients within clinics. We will also explore non-parametric methods such as quantile regression or other rank-based approaches. As noted above, randomization should obviate the need for any additional covariate adjustment, but we will explore whether adjustment for clinic-level characteristics (e.g., clinic size) and provider-level characteristics (e.g., provider demographics and panel size) is necessary. We will use standard assessments of goodness-of-fit, including residual plots, to evaluate the models. Finally, in addition to reporting the treatment difference in terms of the odds ratio from the logistic regression, we will report absolute risk difference as well.

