The secondary outcome of TBQ score, transformed into a binary outcome using an appropriate threshold (e.g., the median) will also be assessed using generalized logistic mixed models as described above; the treatment group (CON vs INT) will be the primary fixed effect of interest, with practice included as a random effect. As with the primary outcome, we will assess the need for adjustment using demographic or clinical characteristics, and will evaluate goodness-of-fit using standard approaches. We will also evaluate the TBQ as a continuous score using a linear mixed model. We will assess the validity of the linearity assumption, and seek a suitable transformation of the TBQ score if it appears to be violated. The statistical power for this analysis will be greater than that for the binary version of the outcome because of the additional information provided when using the scale in its original form.

Health care utilization outcomes will be analyzed using similar generalized linear mixed models; indicators of use will employ the logistic link function, and counts of days in various facility types will employ Poisson regression with the log link function. Treatment burden (using the Treatment Burden Scale) and dementia symptoms/cognitive function (using the DSRS) will also be evaluated as important secondary outcomes. We will have repeated assessments of these items at 6, 12, and 24 months, and will apply longitudinal mixed effects models to evaluate the trajectories and assess whether they differ by treatment group. Specifically, we will model time using indicator variables, and include interaction terms between time indicators and treatment group (CON vs INT); the statistical significance of the coefficients of the interaction terms will indicate whether

the trajectories in the outcomes over time differ by treatment group. We will also explore more parsimonious ways of modeling time, for example as a linear or polynomial effect. We will choose link functions that address ordinal outcomes, such as the log link for ordered categorical outcomes, in the context of proportional odds or multinomial logistic regression.

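### Prior utilisation is collected from the same sources as the H3 outcomes, but Section 7 does not pre-specify it as a covariate in the utilisation models

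*Combined protocol and SAP*

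**What the plan says.** Section 7 (Data Analysis) on utilisation: "Health care utilization outcomes will be analyzed using similar generalized linear mixed models; indicators of use will employ the logistic link function", with Poisson models for days in facilities. The primary model they resemble has treatment group as the fixed effect of interest and practice as a random effect.

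On covariates, Section 7 takes the view that randomisation makes further adjustment unnecessary. It allows three departures:
- Factors that look unbalanced between arms are considered for adjustment, in a sentence about the primary analyses. Baseline TBQ is among its examples; prior utilisation is not.
- Clinic-level and provider-level characteristics are explored.
- For TBQ, the need to adjust for demographic or clinical characteristics is assessed, with no rule given.

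On data, Section 5.4 says "Utilization variables will be measured at 6, 12, 24 months; the baseline measures include a 20 month look back at utilization". Table 1 has rows for prior non-acute use and prior acute use, the latter recorded as "Counts: ED, hospital visits / bed days", and labels both as one year. The note under the table says "Baseline utilization variables will have 20 month look-back through claims and EHR". The outcomes (ED, hospital, SNF and ambulatory use) also come from EHR and claims.

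Utilisation is H3, labelled secondary in Section 1.1, and falls under the Exploratory Aim in Section 1.2.

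**The concern.** Prior use of the same type is a baseline measurement of the outcome itself. It can be cut off before the programme reaches a clinic, so the panel manager cannot have influenced it. Leaving its use to a balance check has two weaknesses. Imbalance does not select for prognostic strength, so a useful covariate is usually left out. When it is admitted, the choice follows inspection of the data.

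The second consideration is recruitment. Clinics are randomised and dyads enrol afterwards, through steps that are not identical by arm. PCP review of the patient list is described for INT clinics (Section 5.1, Level 3). INT providers receive monthly lists, whereas CON providers receive one initially (Section 4). Section 5.2 labels the patient letter as an INT step, although Section 5.1 reads as if letters go to both arms. Randomising about 18 clinics therefore does not guarantee similar habitual use among enrolled patients, and an unadjusted contrast would carry any difference through.

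**Working it through.** The plan gives no power, event rate, correlation or ICC for utilisation, so there is no figure to reproduce. The question is how much a prior-use term could add, over stated assumptions.

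**Inputs from the documents.** "All hypothesis testing will be two-sided and conducted using a significance level of 0.05" (Section 7). 1,000 patients, 500 per arm (Section 1.1). "We will assign two PMs to 9 randomly selected INT clinics" (Section 4), with 9 CON clinics (Section 3.1), so K = 18 and m = 1,000/18 = 55.6. Section 3.1 also says 20 practices; K = 20, m = 50 changes the gains below by at most 0.3 points.

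**Assumed.** Correlation ρ between prior and later use 0.2 to 0.5; ICC 0.01 to 0.05; unadjusted power 80% or 50%; full enrolment without attrition.

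**1. All outcome variance open to explanation.** Power = Φ((1.960 + z_p)/√(1 − ρ²) − 1.960), where z_p = 0.842 for 80%. At ρ = 0.5: 2.802/0.866 − 1.960 = 1.275, giving 89.9%. At ρ = 0.2, 0.3 and 0.4: 81.6%, 83.6% and 86.4%.

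**2. Clustered version.** Design effect DE = 1 + (m − 1)·ICC. The within-clinic share of the variance of a clinic mean is w = (1 − ICC)/DE. If prior use explains only within-clinic variance, the variance is multiplied by 1 − ρ²w; if it explains both levels, by 1 − ρ². For ICC 0.02: DE = 1 + 54.6 × 0.02 = 2.09 and w = 0.98/2.09 = 0.47, so at ρ = 0.5 the factor is 1 − 0.25 × 0.47 = 0.88. With the non-central t on 16 df, the gains in points from 80% are:

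| | ρ 0.2 | ρ 0.3 | ρ 0.4 | ρ 0.5 |
|---|---|---|---|---|
| Within only, ICC 0.05 | 0.4 | 0.9 | 1.6 | 2.5 |
| Within only, ICC 0.02 | 0.7 | 1.7 | 3.0 | 4.6 |
| Within only, ICC 0.01 | 1.0 | 2.3 | 4.1 | 6.3 |
| Both levels | 1.6 | 3.6 | 6.3 | 9.9 |

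From 50% power, the largest entry (both levels, ρ = 0.5) becomes 11.9.

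**3. Binary indicator, simulated** (18 clinics of 56, 1,500 runs per setting, clinic-level test with and without prior use):
- No clinic variance: 81.9 to 82.3% at correlation 0.14; 77.1 to 79.5% at 0.28; 67.5 to 76.3% at 0.40; 60.1 to 73.1% at 0.50.
- Clinic SD 0.25 on the logit scale: 86.1 to 86.3%, 83.7 to 85.3%, 80.7 to 84.6% and 73.6 to 80.9% at correlations 0.14, 0.27, 0.39 and 0.49.

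**4. Counts, simulated** (9 v 9 clinics of 55, mean 1 event in CON, rate ratio 0.75, 1,500 runs per setting, clinic-mean t-test). Patient log-frailty SD is 0.5 or 0.9, and clinic log-SD 0.1 or 0.2. What is varied is how far clinic differences before the trial persist into follow-up:

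| Pre/post correlation of clinic effects | 0.5, 0.1 | 0.5, 0.2 | 0.9, 0.1 | 0.9, 0.2 |
|---|---|---|---|---|
| 1 | 81 to 85% | 57 to 67% | 62 to 72% | 42 to 62% |
| 0.5 | 78 to 80% | 57 to 61% | 62 to 69% | 45 to 53% |
| 0 | 80 to 80% | 56 to 56% | 61 to 64% | 42 to 43% |

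The large gains depend on clinic differences that persist fully.

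**5. Would the balance rule find it?** In the same kind of simulation, a patient-level Wilcoxon test (one of those Section 7 lists) flagged prior use in 8 to 19% of trials. The covariate would usually stay out.

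**The case against.** A reader might infer that the plan excludes prior use. It does not. Section 5.4 calls its baseline measures control variables and says that some come from claims. It also lists utilisation in the prior year among patient characteristics. The balance list in Section 7 is open-ended, and utilisation models resembling those for TBQ could inherit the TBQ assessment of need. That stands: this is a gap in pre-specification. It does not close the gap, because none of these passages assigns prior use to a utilisation model, and the imbalance rule is worded for the primary analyses and promises only consideration.

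A reader might also infer that a strong predictor and several points of power are being lost. The documents contain no figure for either. Several points needs a correlation of roughly 0.3 to 0.4 or more, together with a low ICC or clinic differences that persist.

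Nor do the documents show that recruitment has biased the utilisation contrast. They show only that enrolment follows allocation and that some steps differ.

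Finally, the simulations use clinic-level tests rather than the planned mixed models. The clinic-mean test kept its false-positive rate between 0.036 and 0.059. A Poisson model with only a practice random effect, fitted to the same kind of null data, rejected in 9.5 to 12.5% of trials (400 per setting, Wald test). The first range therefore cannot be used to vouch for the planned model.

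**Conclusion.** The concern holds as a specification gap. Prior use is planned for collection from the outcome sources, and Section 7 gives it no fixed role in the utilisation models. Adjusting for it would probably improve precision and would reduce the effect of any arm difference in habitual use.

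The size cannot be fixed from the documents. From 80% power with ρ between 0.2 and 0.5, the gain runs from 0.4 points (ICC 0.05, within-clinic variance only) to 9.9 (both levels explained). Larger gains appear only from lower starting power, and then only where clinic differences persist or are very small. All of this rests on assumed correlations, ICCs and full enrolment. It bears on a secondary or exploratory outcome and leaves the primary HbA1c analysis untouched.

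**What to change.** 1. Reconcile the one-year label in Table 1 with the 20-month look-back in its note and in the text. Use a single window for all patients, ending before the clinic's programme start or the patient's enrolment, whichever is earlier. Table 1 also ticks prior use at 6, 12 and 24 months; only the baseline value should serve as the covariate.
2. State in Section 7 that each utilisation model includes prior use of the same type as a fixed covariate, whatever the balance tests show: for example log(1 + prior count or days) for counts, and prior any-use for indicators.
3. Keep the unadjusted model as a sensitivity analysis.
4. Give a missing-data rule for patients new to the clinic or without linked claims. Both arms are refreshed with such patients (Section 4).
5. In the logistic models the adjusted odds ratio is conditional on prior use, so report the risk difference beside it.

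No new data type is needed; the cost is SAP wording, one extra term per model and the missing-data rule. Section 5.4 has the claims application in year 2 or 3, so this may still be settled before claims outcomes are seen.

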- **Social Support MOS-5.** This survey instrument has been used to investigate social support for caregivers of dementia patients and is well studied. It has 5 questions.
- **Global Health (Promis Scale v1.2):** This commonly used instrument from the Promis series of instruments assesses the general health of the caregiver and is reported by the caregivers. It has 10 questions.
- **Diabetes Caregiver Distress Scale:** This scale is adapted from the diabetes distress scale. We were unable to find a diabetes care distress or care burden scale that is directed at caregivers, even when checking literature for type 1 diabetes and children with diabetes. We therefore will use this instrument for caregivers although it is usually given to patients. It has 7 questions.
- **Mental Health and Substance Use:** These 5 questions ask about caregiver history of mental health, including stress and depression, alcohol and illicit drug use.
- **Treatment Burden Questionnaire (TBQ):** This instrument has been used in studies with patients but not with caregivers who are supervising or providing care for care-patients (patients). The form has 15 questions. In order to publish our findings, we are working with experts to conduct psychometric evaluation to validate the TBQ for use with caregivers.
- **Dementia Severity Rating Scale (DSRS):** This is a caregiver questionnaire that asks about the patient's dementia characteristics. It has been used in many studies, including studies by our group, and is well validated. This scale includes questions related to the patient's functional ability.
- **COVID Questionnaire:** This instrument assesses the impact of COVID-19 pandemic and its associated mitigation efforts on study subjects. Specifically, it includes COVID-19 status, related symptoms, and the social, medical and functional impact of the pandemic on caregivers and care recipients. We will attempt to complete this instrument at least once (baseline or follow-up) with every caregiver/care recipient dyad.
- **Follow-up COVID Questionnaire:** This survey will capture any changes that may have occurred since the first COVID survey and will be administered to any participant that has already completed an initial survey.

Most variables measured by EHR and claims are self-explanatory. However, two other instruments will be used with EHR and claims.

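### Section 7 plans a DSRS trajectory over 6, 12 and 24 months, but the only Table 1 row naming the DSRS schedules baseline and 24 months, and the four-wave dementia-symptoms row uses an undefined DSS

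*Combined protocol and SAP*

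**What the plan says.** Section 7 (Data Analysis) states that "dementia symptoms/cognitive function (using the DSRS) will also be evaluated as important secondary outcomes" and, of treatment burden and dementia symptoms together, "We will have repeated assessments of these items at 6, 12, and 24 months". Time enters as indicators with arm interactions, and the significance of the interaction coefficients decides whether the trajectories differ. It adds: "We will also explore more parsimonious ways of modeling time, for example as a linear or polynomial effect".

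Table 1 (Measures, under Section 5.4) has three relevant rows:

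- Dementia Severity, measured by the "Dementia Severity Rating Scale": marked at baseline and 24 months, with the 6- and 12-month cells empty.
- "Dementia symptoms", among the outcome measures: instrument given as DSS, marked at all four waves.
- Functional State: "14 items: ADL/ IADL for CG; within DSS for Pt", marked at all four waves.

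DSS is not expanded in the List of Abbreviations, the Table 1 legend or the instrument descriptions. Those descriptions include the DSRS, of which they say "This scale includes questions related to the patient's functional ability", and no other dementia scale. The outcome text after Table 1 places caregiver-reported outcomes at 0, 6, 12 and 24 months and says "Dementia and diabetes specific outcomes include: a) patient dementia symptoms", without naming an instrument. Section 3.4 confirms that a baseline survey is taken.

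**The concern.** The analysis stated for Aim 4 and the schedule stated for the scale it names cannot both be followed. Two analysts could use different waves, different dyads and possibly different scales for the same aim, and each could claim to have followed the plan.

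The schedule also determines who contributes. Section 4 refreshes the sample in both arms with newly diagnosed and new patients. For the intervention clinics it says that these dyads have shorter follow-up but still supply data until the study ends. On a two-wave DSRS schedule, a dyad that never reaches month 24 supplies no follow-up DSRS at all.

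A related gap affects every outcome in the longitudinal model, including the TBQ. Section 7 lists only post-baseline waves, does not say whether baseline is modelled, and names neither a joint test of the interactions nor a single contrast. Whether a real benefit shows up in the planned test can depend on that choice.

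**Working it through.** The plan gives no figure for the DSRS to reproduce. The check asks which coefficients each schedule can identify.

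**1. Rank of the arm-by-time model.** With *k* time terms, the fixed part has an intercept, an arm term, *k* time terms and *k* interactions, so 2 + 2*k* columns. Two arms at *w* waves give 2*w* cell means, so the rank cannot exceed 2*w*. With baseline as a modelled wave:

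| Time model | Waves 0, 6, 12, 24 | Waves 0, 24 |
|---|---|---|
| Indicators (*k* = 3) | 8 columns, rank 8; 3 of 3 interactions estimable | 8 columns, rank 4; 1 of 3 estimable |
| Linear (*k* = 1) | 4 columns, rank 4; 1 of 1 | 4 columns, rank 4; 1 of 1 |
| Quadratic (*k* = 2) | 6 columns, rank 6; 2 of 2 | 6 columns, rank 4; neither separately |

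On waves 0 and 24 the surviving indicator interaction is the arm difference in change from baseline to month 24, and the linear model gives the same contrast. In the quadratic model, with *s* = *t*/24, *s* and *s*² are both 0 at baseline and both 1 at month 24. Only the sum of the two interactions is identified, and that sum is again the 24-month difference in change.

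If baseline is a covariate instead, waves 6, 12 and 24 give 6 columns, rank 6 and 2 of 2 interactions. Month 24 alone gives rank 2 and 0 of 2, leaving one arm difference at month 24.

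**2. Baseline in or out, with waves 6, 12 and 24 available.** Take an arm difference of 0 at baseline and *d* at months 6, 12 and 24. Each interaction is the difference at month *t* minus the difference at the reference month.

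- Reference month 0: interactions *d*, *d*, *d*.
- Baseline omitted, reference month 6: *d* − *d* = 0 and *d* − *d* = 0. The effect appears only in the arm main effect.

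**3. Late entrants.** If surveying ends at month *E* after enrolment opens, the last entry with a 24-month survey is at month *E* − 24. With even enrolment over *L* months, the share without one is max(0, (*L* − *E* + 24)/*L*). The documents give neither *E* nor *L*, so these are assumptions:

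- *E* = 36 (Section 4 speaks of the study's three years): *L* = 12, 18, 24 gives 0, 6/18 = 33%, 12/24 = 50%.
- *E* = 48 (Section 8.2 distinguishes the first three years from a last year): 0% for all three.

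The direction follows from the schedule. The size does not follow from anything in the documents.

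**The case against.** The strongest reply is that the harmful reading is the less likely one. The outcome row, the outcome text and Section 7 all have dementia symptoms assessed at the follow-up waves. The conflicting row is headed severity, which the text after Table 1 treats as a patient characteristic. Patient function is said to sit within DSS, and the DSRS is the only dementia scale described and covers function. On that reading DSS is a slip for DSRS, a corrected label and two added marks resolve the conflict, and the Section 7 model stands. I accept that this is the probable reading. It does not close the point, because the one scale would still have two schedules in the same table and no text says which governs. Nor can the legend be relied on to settle it, since it expands abbreviations (HABC-M, MYLOH) that have no row.

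Two stronger readings should be resisted. A reader might infer that Aim 4 cannot be tested on the printed schedule. It can: Aim 4 asks whether symptoms worsen less, and the 24-month difference in change answers that. Polynomial time is only an exploratory option. A reader might also infer that a third or a half of dyads would drop out of the analysis. Those shares depend on an assumed end of surveying, and a later end removes them.

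On baseline, it is fair to say that it is collected, that a trajectory would naturally include it, and that a sustained effect would still show in the arm main effect. Section 7 also makes the arm term the effect of interest in its separate TBQ model. What remains is that the longitudinal test is defined by the interaction coefficients, without stating the reference or how they are combined.

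**Conclusion.** The inconsistency is real and should be corrected; it concerns secondary outcomes. Section 7 assumes three post-baseline DSRS assessments, while the only row naming the DSRS provides one. If that row is right, 1 of 3 planned interactions is estimable with baseline modelled. The 24-month difference in change survives, and the 6- and 12-month contrasts and curvature do not. If DSS is the DSRS and four waves are collected, all three are estimable and the error lies in the table. The documents make the second more likely without establishing it, and they do not support saying that Section 7 names the wrong scale.

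The rank results need no assumption beyond the schedules. The zero-interaction result assumes that baseline is omitted and that the effect is complete by month 6 and constant afterwards. The number of late entrants affected is unknown.

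The primary HbA1c analysis is untouched. Caregiver-perceived care quality, which the outcome text calls the main caregiver-reported outcome but which has no described instrument and no Section 7 analysis, is a separate matter to raise on its own.

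**What to change.** By a dated amendment before arm-level results are seen:

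1. State whether DSS is the DSRS. Make the Dementia Severity, Functional State and Dementia symptoms rows, the outcome text and Section 7 agree on one scale and one schedule for Aim 4.
2. If the DSRS is collected at baseline and 24 months only, replace the trajectory model with 24-month DSRS adjusted for baseline DSRS, with clinic as a random effect. Report by arm the number of dyads without a 24-month survey.
3. If it is collected at four waves, state that baseline is in the model and pre-specify either the 24-month contrast or a joint test of the interactions. Refreshed dyads then contribute the waves they reach. Make the same statement for the TBQ.
4. As a free improvement rather than a correction, lead with the continuous TBQ model that Section 7 already plans and itself describes as more powerful. Adjust it for the baseline TBQ already collected, and keep the median split as supportive.

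The cost is one amendment to Section 7, Table 1 and the outcome text, with sponsor agreement and IRB approval (Statement of Compliance; Section 9.2). No survey item, wave or dyad is added.
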